6.3.6 Adverse events based on examinations and tests

The results from protocol mandated laboratory tests and vital signs will be summarised in the clinical study report. Deterioration as compared to baseline in protocol-mandated laboratory values, vital signs should therefore only be reported as AEs if they fulfil any of the SAE criteria or are the reason for discontinuation of treatment with the investigational product.

If deterioration in a laboratory value/vital sign is associated with clinical signs and symptoms, the sign or symptom will be reported as an AE and the associated laboratory result/vital sign

will be considered as additional information. Wherever possible the reporting Investigator uses the clinical, rather than the laboratory term (e.g., anaemia versus low haemoglobin value). In the absence of clinical signs or symptoms, clinically relevant deteriorations in non-mandated parameters should be reported as AE(s).

Any new or aggravated clinically relevant abnormal medical finding at a physical examination as compared with the baseline assessment will be reported as an AE.

6.4 **Reporting of serious adverse events**

All SAEs have to be reported, whether or not considered causally related to the investigational product, or to the study procedure(s). All SAEs will be recorded in the CRF.

If any SAE occurs in the course of the study, then Investigators or other site personnel inform the appropriate AstraZeneca representatives within one day i.e., immediately but **no later than 24 hours** of when he or she becomes aware of it.

The designated AstraZeneca representative works with the Investigator to ensure that all the necessary information is provided to the AstraZeneca Patient Safety data entry site within 1 calendar day of initial receipt for fatal and life threatening events and within 5 calendar days of initial receipt for all other SAEs.

For fatal or life-threatening adverse events where important or relevant information is missing, active follow-up is undertaken immediately. Investigators or other site personnel inform AstraZeneca representatives of any follow-up information on a previously reported SAE within one calendar day i.e., immediately but **no later than 24 hours** of when he or she becomes aware of it.

Once the Investigators or other site personnel indicate an AE is serious in the WBDC system, an automated email alert is sent to the designated AstraZeneca representative.

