8.5.2 Analysis of the secondary and additional variables

For the open-label initial phase, the mean and relative reduction in the secondary efficacy endpoints will be evaluated for all enrolled patients. The change from baseline will be assessed using a paired t-test, and a two-sided p-value ≤ 0.05 will be considered statistically significant.

The methods used to evaluate the secondary efficacy endpoints, for the 28-day randomized treatment study phase; to compare each active dose (high to low) vs. placebo control will be describe in the SAP.

Secondary efficacy endpoints will include:

- The proportion of patients who remain normokalemic (as defined by S-K between 3.5-5.0 mmol/L, inclusive) at the end of the 28-day randomized treatment study phase and during the 28-day randomized treatment study phase
- The number of days patients remain normokalemic during the 28-day randomized treatment study phase
- The mean change and mean percent change in S-K levels evaluated relative to both baselines
- The time to hyperkalemia (defined as $S-K \ge 5.1 \text{ mmol/L}$)
- The mean change in S-Aldo and P-Renin levels

In addition, the secondary efficacy endpoint at the end of the 28-day randomized treatment study phase will be evaluated in patients with hyperkalemia (defined as S-K \geq 5.1 mmol/L) for the subgroups defined in Section 8.5.4. More details will be specified in the SAP.

Sensitivity analysis

Sensitivity analyses of the primary efficacy analysis and secondary efficacy analysis of the proportion of normokalemic patients at the end of and during the 28-day randomized treatment study phase will be performed to assess the robustness of the primary and these key secondary results. Details will be provided in the SAP.

Separate safety analyses will be performed for the open-label initial phase and the 28-day randomized treatment study phase. Safety endpoints will include adverse events (AEs), serious AEs (SAEs), vital signs (VS), physical examinations, ECGs, clinical laboratory evaluations, and other electrolytes (specifically, serum calcium [S-Ca], serum magnesium [S-Mg], serum sodium [S-Na], serum phosphate [S-PO4], serum bicarbonate [S-HCO3], and blood urea nitrogen [BUN]).

Hypokalemia will be analyzed based on laboratory values and not by specific MedDRA terms.

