The respective safety analysis will be undertaken on the safety analysis sets, separately for the open-label initial phase and for the 28-day randomized treatment study phase. Safety and tolerability data will be presented by treatment arm. Where appropriate, the safety analyses will include descriptive statistics, counts and percentages. More details will be described in the SAP. Only AE with date of onset during the respective observation period will be presented. Laboratory data and other investigations will be presented descriptively. More information will be provided in the SAP.

Adverse events will be classified according to Medical Dictionary for Regulatory Activities (MedDRA [latest version]). The type, timing (onset, duration), relationship, and severity of AEs will be reported. Withdrawal due to AEs will also be reported. Narratives will be written for every AE classified as serious or leading to withdrawal of IP. Safety results will be displayed separately for each of these phases.

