9.4 Data management by AstraZeneca or delegate

Data management will be performed by AstraZeneca Data Management Center staff or other party, according to the Data Management Plan.

Clinical Study Protocol Drug Substance ZS Study Code **D9480C00001** Version **6.0** Date **19** August 2020

Data will be entered into the WBDC system at the study site. Trained site staff will be entering the data as specified in the protocol and according to the eCRF instructions. Data entered into the WBDC system will be immediately saved to a central database and changes tracked to provide an audit trail. The data will then undergo quality control and be validated as described in the Data Management Plan.

AEs and medical/surgical history will be classified according to the terminology of the latest version the Medical Dictionary for Regulatory Activities (MedDRA). Medications will be classified according to the World Health Organization Drug (WHODrug) Dictionary (version will be designated in the clinical study report). Classification coding will be performed by the Medical Coding Team at the AZ Data Management Center or other party.

The data collected through third party sources will be obtained and reconciled against study data.

Data queries will be raised for inconsistent, impossible or missing data. All entries to the study database will be available in an audit trail.

The PI is responsible for signing the eCRF and this may be delegated to a trained Investigator.

Quality control procedures will be applied to each stage of data handling to ensure that all data are reliable and have been processed correctly. The Data Management Plan will also clarify the roles and responsibilities of the various functions and personnel involved in the data management process.

When all data have been coded, validated, signed and locked, clean file will be declared. Any treatment revealing data may thereafter be added and the final database will be locked. A copy of the eCRF will be archived at the study site when the study is completed.

Serious Adverse Event (SAE) Reconciliation

SAE reconciliation reports are produced and reconciled with the Patient Safety database and/or the investigational site.

Data associated with human biological samples

Data associated with biological samples will be transferred from laboratory(ies) external to AstraZeneca.

Management of external data

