4.3.2 Adverse Events

4.3.2.1 Definitions and Derivations

On-treatment adverse events are defined as per Section 3.3.1.2.

The derivations for the following parameters will be the difference between the two dates stated below + 1 day (where first dose date is for either the OLP or RTP first dose date as applicable).

- Time from start of treatment to onset of AE (days)
- Time from last dose to death (days)
- Time from first dose to death (days)
- Time from last dose to onset of AE (days) Calculated for AEs starting after the discontinuation of the study treatment.
- Time from start of treatment to AE becoming serious (days)
- Time from start of treatment to discontinuation of investigational product (due to adverse event) (days).

MedDRA (using the latest or current version) is used to code AEs apart from hypokalemia. The identified risk of hypokalaemia is defined by laboratory values and not by specific MedDRA terms.

Oedema

Oedema related events will be defined by the following MedDRA PT terms: Hypervolaemia Fluid retention, Generalised oedema, Localised oedema, Oedema, Oedema peripheral, Peripheral swelling.

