4.3.2.2 Presentation

Adverse Events will be presented separately for the OLP and the RTP. The analyses will mainly be focused on on-treatment AEs, but some tables will be replicated for all AEs occurring during a study period. All adverse events will be summarized by SOC and PT. All AEs, including those not considered on-treatment, will be included in safety listings but excluded from the summary tables.

The onset date of the AE determines the phase in which the AE will be summarized. This is in order to have a consistent "worst case" allocation of AEs, because it will not be possible to distinguish AEs occurring before or after the actual intake of randomized IP.

Overall Summary of Adverse Events

AEs will be summarised by treatment group for the OLP and RTP and will include the following:

- the number and percentage of subjects experiencing an AE
- the number and percentage of subjects experiencing an AE with an outcome of death
- the number and percentage of subjects experiencing a SAE
- the number and percentage of subjects experiencing an AE leading to treatment withdrawal

This table will be done both on-treatment and using all AEs that occurred during RTP.

AEs and SAEs by System Organ Class (SOC) and Preferred Term (PT)

The number and percentage of subjects with AEs and SAEs will be summarised by SOC and PT, by treatment group. A subject with more than one type of AE in a particular SOC will be counted only once in the total of subjects experiencing AEs in that particular SOC. Since a subject could have more than one type of AE within a particular SOC, the sum of subjects experiencing different AEs within the SOC could be larger than the total number of subjects experiencing AEs in that SOC. Similarly, a subject who has experienced an AE in more than one SOC will be counted only once in the total number of subjects experiencing AEs in all SOCs.

AEs by PT and frequency

The number and percentage of subjects with AEs will be summarised by PT and treatment group and sorted by descending frequency on PT level.

Possibly related AEs and SAEs by SOC and PT

The number and percentage of subjects with possibly related AEs and SAEs will be summarised by SOC, PT, and treatment group.

AEs by SOC, PT, and maximum severity

The number and percentage of subjects with AEs will be summarised by SOC, PT and maximum intensity, and treatment group.

Deaths

The number and percentage of subjects with SAEs or AEs with outcome of death will be

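### SAP 4.3.2.1 exempts hypokalaemia from MedDRA coding, which contradicts SAP 4.3.2.2 and the protocol's coding rules

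*SAP*

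**What the plan says.** Two statements stand next to each other in SAP Section 4.3.2.1. The first is that MedDRA "is used to code AEs apart from hypokalemia". The second is: "The identified risk of hypokalaemia is defined by laboratory values and not by specific MedDRA terms".

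SAP Section 4.3.2.2 then states, with no exception: "All adverse events will be summarized by SOC and PT". It plans by-arm tables of AEs and SAEs by SOC and PT, AEs by PT in descending frequency, possibly related AEs and SAEs, AEs by maximum severity, and deaths. It also plans an overall table that counts patients with any AE, an AE with outcome death, an SAE, or an AE leading to treatment withdrawal.

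The protocol's safety analysis text (8.5.3 in its table of contents) says: "Hypokalemia will be analyzed based on laboratory values and not by specific MedDRA terms". The same text says: "Adverse events will be classified according to Medical Dictionary for Regulatory Activities". Protocol Section 9.4 repeats the coding rule for data management: "AEs and medical/surgical history will be classified according to the terminology of the latest version the Medical Dictionary for Regulatory Activities". Neither coding statement carves out a term.

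Protocol Section 6.3.6 limits which laboratory changes become AEs. Of deteriorations in protocol-mandated tests it says that they "should therefore only be reported as AEs if they fulfil any of the SAE criteria or are the reason for discontinuation of treatment".

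**The concern.** Defining a risk by laboratory values and leaving a reported event uncoded are different instructions. The protocol gives the first; the SAP adds the second. An event without a code has neither SOC nor PT, so a table indexed by SOC and PT has no row for it.

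The events at issue are not trivial ones. Under protocol Section 6.3.6 an isolated low potassium becomes an AE only when it is serious or is why treatment stopped. Stopping for this reason is foreseen: Sections 3.9 and 7.2 discontinue patients with a confirmed potassium below 3.0 mmol/L. Hypokalaemia is also one of the two identified risks named in protocol Section 1.3.3. What is at stake is whether its reported cases are visible by arm and by term, with seriousness and relatedness, in the study's standard AE tables.

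**Working it through.** No figure in the plan depends on the coding rule, so the check is a comparison of texts.

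**1. Does the protocol support the exemption?** The protocol's hypokalaemia sentence governs analysis. Its two coding sentences cover AEs without exception. The second SAP sentence quoted above already implements the analysis rule in full. The exemption in the first SAP sentence therefore adds something the protocol does not contain. SAP Section 2, which lists changes to the protocol-planned analyses, does not mention it.

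**2. Is the SAP consistent with itself?** Section 4.3.2.1 leaves hypokalaemia AEs uncoded. Section 4.3.2.2 summarises all AEs by SOC and PT. A programmer cannot follow both.

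**3. What drops out if 4.3.2.1 is followed?** All the SOC/PT tables and the PT frequency table need a code; the overall table does not. If the total rows of the SOC/PT tables are built from coded records, then for each arm and each type of event:

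overall count − SOC/PT total = number of patients whose only event of that type is an uncoded one.

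As an illustration, take a patient whose single AE is hypokalaemia that stopped treatment. That patient adds 1 to the overall AE row and 1 to the withdrawal row, and 0 to the SOC/PT total. A patient who also has a coded AE leaves the totals equal, but the hypokalaemia row is still missing. The current SAP plans no SOC/PT table of AEs leading to withdrawal. For a non-serious, treatment-stopping case, the general AE tables are thus the only planned by-arm display at term level.

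**4. Where would the events still be seen?**
- In the overall AE, SAE, death and withdrawal counts (SAP 4.3.2.2).
- In the AE listings and the listing of deaths (SAP 4.3.2.2).
- In narratives, which the protocol's safety analysis text requires for every AE that is serious or leads to withdrawal of study drug.
- In the laboratory table of SAP 4.3.3.2, which counts patients below 3.5, 3.0 and 2.5 mmol/L on treatment, by phase and treatment group.

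**5. Is the laboratory table a substitute?** It covers more hypokalaemia than AE reports can, but it carries no seriousness, causality, intensity, outcome or discontinuation. Its values come from the central laboratory, with adjusted i-STAT only where those are missing (SAP 3.3.5), while stopping is decided on i-STAT (protocol 3.9). Its window closes one day after the last dose (SAP 3.3.1.2). A reported case will usually have a matching laboratory row, but need not.

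**6. How many events?** Protocol Section 1.3.2 gives 4.1% of ZS patients below 3.5 mmol/L in earlier trials. With 100 planned patients in each ZS arm, 0.041 × 200 = 8.2 patients. Figure 2 shows 9.8 for 10 g, with no unit in the available text and no statement of whether it is a rate or a difference from placebo. If it is a percentage rate, it applies to the 10 g arm only: 0.098 × 100 = 9.8. Adding 0.041 × 100 = 4.1 for 5 g gives 13.9. These are patients with a low laboratory value, not AEs. The documents do not say what share is serious or stops treatment, so no count of affected AEs follows.

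**The case against.** The strongest reply is that this is loose drafting with a clear intent. The sentence after the exemption defines the risk by laboratory values, and the text then defines oedema, the other identified risk, by a list of PTs. Read together, the section says how each risk is identified, as the protocol asks. Coding is assigned in protocol Section 9.4 to the medical coding team or another party, and the SAP refers to the protocol for study conduct, so the coding will probably be done regardless. This stands as an account of intent. It does not remove the literal instruction or the conflict with Section 4.3.2.2.

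Four stronger readings are tempting and are not supported:
- A reader might infer that hypokalaemia AEs are definitively excluded from the SOC/PT tables. Section 4.3.2.2 includes all AEs, so the SAP contradicts itself rather than settling on exclusion.
- A reader might infer that the events are lost from reporting. They stay in the counts, listings and narratives, and largely in the laboratory table; in the randomised phase every potassium sample goes to both i-STAT and the central laboratory (protocol Table 2, note 6).
- A reader might infer that only serious or treatment-stopping cases can be reported. Protocol Section 6.3.5 prefers a diagnosis to a list of symptoms, so symptomatic hypokalaemia could also be recorded under that term.
- A reader might apply Figure 2's 9.8 to all 200 ZS patients. It belongs to the 10 g arm of 100.

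**Conclusion.** Wrong as written, minor. The coding exemption goes beyond the protocol, is not declared as a change, and conflicts with the SAP's own presentation rule. If it is followed literally, AEs reported as hypokalaemia, mainly serious or treatment-stopping cases, have no row in the by-arm SOC/PT tables, and those tables may not reconcile with the overall counts.

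The conclusion rests on the literal wording, since the intent was probably only to define the risk by laboratory values. The number of events affected is not derivable from the documents and is probably small. Efficacy results, power and type I error do not depend on it, and the laboratory analysis of the risk remains intact.

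**What to change.** In SAP Section 4.3.2.1, delete the last three words of "is used to code AEs apart from hypokalemia". Every reported AE, including any reported as hypokalaemia, is then coded in MedDRA and shown in the SOC/PT tables. Keep the following sentence, which defines the identified risk by laboratory values, and keep the laboratory table (<3.5, <3.0, <2.5 mmol/L) as the main analysis of that risk.

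The cost is a three-word deletion, best made before the AE tables are programmed. The coding itself is already required by the protocol, and no new data or analyses are needed.

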4.3.2.2 Presentation

Adverse Events will be presented separately for the OLP and the RTP. The analyses will mainly be focused on on-treatment AEs, but some tables will be replicated for all AEs occurring during a study period. All adverse events will be summarized by SOC and PT. All AEs, including those not considered on-treatment, will be included in safety listings but excluded from the summary tables.

The onset date of the AE determines the phase in which the AE will be summarized. This is in order to have a consistent "worst case" allocation of AEs, because it will not be possible to distinguish AEs occurring before or after the actual intake of randomized IP.

Overall Summary of Adverse Events

AEs will be summarised by treatment group for the OLP and RTP and will include the following:

- the number and percentage of subjects experiencing an AE
- the number and percentage of subjects experiencing an AE with an outcome of death
- the number and percentage of subjects experiencing a SAE
- the number and percentage of subjects experiencing an AE leading to treatment withdrawal

This table will be done both on-treatment and using all AEs that occurred during RTP.

AEs and SAEs by System Organ Class (SOC) and Preferred Term (PT)

The number and percentage of subjects with AEs and SAEs will be summarised by SOC and PT, by treatment group. A subject with more than one type of AE in a particular SOC will be counted only once in the total of subjects experiencing AEs in that particular SOC. Since a subject could have more than one type of AE within a particular SOC, the sum of subjects experiencing different AEs within the SOC could be larger than the total number of subjects experiencing AEs in that SOC. Similarly, a subject who has experienced an AE in more than one SOC will be counted only once in the total number of subjects experiencing AEs in all SOCs.

AEs by PT and frequency

The number and percentage of subjects with AEs will be summarised by PT and treatment group and sorted by descending frequency on PT level.

Possibly related AEs and SAEs by SOC and PT

The number and percentage of subjects with possibly related AEs and SAEs will be summarised by SOC, PT, and treatment group.

AEs by SOC, PT, and maximum severity

The number and percentage of subjects with AEs will be summarised by SOC, PT and maximum intensity, and treatment group.

Deaths

The number and percentage of subjects with SAEs or AEs with outcome of death will be

summarised by SOC, PT, and treatment group. Subject listings of all deaths and their causes will be provided.

Oedema

The number and percentage of subjects with oedema related events will be presented by treatment group, separately for OLP and RTP.

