6.3 Recording of adverse events

6.3.1 Time period for collection of adverse events

Adverse Events will be collected from the time of main study informed consent, throughout the treatment period and including the EOS visit. SAEs will be collected from the time of optional Pre-screening informed consent, throughout the treatment period and including the EOS visit.

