3.3.1.2 Definition of On-Treatment

For OLP: Any measurements that have an onset day on or after the date of first dose of openlabel study treatment and no later than the date of last dose of open-label study treatment + 1 day.

For RTP: Any measurements with an onset date more than one day after the day of last dose of open label study medication, and either on or after the day of first dose of randomized study medication, and no later than the day of last dose of study medication +1 day.

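### SAP 4.3.2.2 contradicts itself on which adverse events enter the summary tables; as it is evidently meant, SAEs and fatal AEs starting more than one day after the last dose are not tabulated by SOC/PT

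*SAP*

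**What the plan says.** **Collection.** Protocol 6.3.1: "Adverse Events will be collected from the time of main study informed consent, throughout the treatment period and including the EOS visit". For SAEs it starts earlier and ends at the same point: "SAEs will be collected from the time of optional Pre-screening informed consent, throughout the treatment period and including the EOS visit".

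**On-treatment window.** SAP 4.3.2.1: "On-treatment adverse events are defined as per Section 3.3.1.2". In that section the window closes, for the randomised treatment phase (RTP), "no later than the day of last dose of study medication +1 day" and, for the open-label phase (OLP), "no later than the date of last dose of open-label study treatment + 1 day".

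**Presentation (SAP 4.3.2.2).** The opening paragraph makes three statements in a row:
- The analysis concentrates on on-treatment AEs, with some tables, not named there, repeated for all AEs in a study period.
- Every AE is summarised by SOC and PT.
- "All AEs, including those not considered on-treatment, will be included in safety listings but excluded from the summary tables".

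The Overall Summary then has four counts of subjects: any AE, an AE with outcome of death, an SAE, and an AE leading to treatment withdrawal. Of this table the SAP says: "This table will be done both on-treatment and using all AEs that occurred during RTP". The tables that follow (AEs and SAEs by SOC/PT, AEs by PT, possibly related events, maximum severity, deaths by SOC/PT) state neither a window nor an all-event version. All deaths and their causes are listed.

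**Protocol analysis text.** The safety analysis part of Protocol Section 8.5 says: "Only AE with date of onset during the respective observation period will be presented". It also requires a narrative for every serious AE and every AE leading to withdrawal of study drug.

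**The concern.** A programmer cannot follow all of Section 4.3.2.2. Its statements on what goes into the summary tables conflict, and taken literally the exclusion sentence removes all AEs from them.

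What is at stake is whether serious and fatal events after the last dose are shown by arm and by diagnosis. Protocol 3.9 stops study drug for, among other reasons, confirmed i-STAT potassium above 6.2 mmol/L, serious arrhythmia and acute heart failure. Patients who stop in the RTP and agree to remain in the study keep their assessments, so later events are collected. Protocol 1.2 says the randomised phase is meant to show that hyperkalemia returns once ZS is withdrawn, and patients in both ZS arms come off drug at or before the end of treatment. The main efficacy analysis follows patients through discontinuation under a treatment policy (SAP 4.2.1.1), while the safety tables by term would end one day after the last dose. SAP 4.3.2.1 even derives the time from last dose to AE onset and to death, but no table by term is specified for those events.

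**Working it through.** The plan states no figure to reproduce. The check has two parts.

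**1. Where an SAE or fatal AE with onset more than one day after the last dose goes, on the evident reading**

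The evident reading is that the exclusion sentence means AEs outside the on-treatment window.

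| Output | RTP | OLP, not randomised |
|---|---|---|
| Overall Summary, on-treatment | no | no |
| Overall Summary, all AEs | yes, by arm, no SOC/PT | not specified |
| SAEs by SOC/PT | no | no |
| Deaths by SOC/PT | no | no |
| Listings | yes | yes |
| Narratives (SAEs) | yes | yes |

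The entries for the two SOC/PT tables rest on the general exclusion sentence, because those tables give no window of their own. The RTP entry for the all-AE Overall Summary assumes that the RTP runs to EOS; SAP Table 2 supports this by placing the Day 35 visit within that phase.

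**2. Length of the untabulated window**

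The last on-treatment day is last dose + 1, so the first day outside is last dose + 2.

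Days outside but under collection = EOS day − (last dose day + 2) + 1 = EOS day − last dose day − 1.

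Inputs:
- Last dose of a completer: Day 28 (28 once-daily doses from Day 1).
- EOS: nominal Day 35, 7 ± 1 days after the last dose, so Days 34 to 36 (Protocol Table 2).
- EOS in a prolonged public holiday: as late as Day 43 (Protocol Table 2).

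Completer:
- Nominal: 35 − 28 − 1 = 6 days, or 6/35 = 17%.
- Range: 34 − 28 − 1 = 5 to 36 − 28 − 1 = 7 days.
- Latest holiday EOS: 43 − 28 − 1 = 14 days.

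Early stop. The documents support two EOS timings:
- EOS counted from the last dose administered (Protocol Table 2, note 9; Protocol 4.4 for patients withdrawn from the study): 6 − 1 = 5 to 8 − 1 = 7 days, whatever the stop day.
- Patient stays in the study to Day 35 (Protocol 3.9; SAP Table 2, note 6, which counts from the last planned dose). The stop days below are assumptions.

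| Assumed last dose | Days outside | Share of 35 days |
|---|---|---|
| Day 22 | 35 − 22 − 1 = 12 | 34% |
| Day 15 | 35 − 15 − 1 = 19 | 54% |
| Day 8 | 35 − 8 − 1 = 26 | 74% |

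OLP patient not randomised: EOS is again 7 ± 1 days after the last dose, so the window is 5 to 7 days.

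**The case against.** The strongest case on the other side is that this is unclear drafting, not a settled exclusion. The SAE and death tables state no window, and the sentence just before the exclusion sends every AE to SOC/PT tables. Post-treatment events are not lost: RTP SAEs and deaths are counted by arm in the all-AE Overall Summary, every death is listed with its cause, every AE is listed, and every SAE has a narrative. With 250 randomised patients, off-treatment serious events may be few enough to read from the listings, though no rate is given. All of this stands, and it limits the point to presentation by arm and term.

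A reader might infer that the one-day cut-off selectively undercounts harm in one arm, because this is a randomised-withdrawal design. The documents do not support that. Withdrawal is studied by randomising to placebo, and events on placebo are on-treatment. A potassium value above 6.2 mmol/L reported as an AE because it caused discontinuation (Protocol 6.3.6) would normally have its onset inside the window and count as an AE leading to withdrawal. Events after the stop may also be confounded by other hyperkalemia treatment, which Protocol 7.7 then allows. The documents give no event rate, discontinuation rate or arm split.

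A reader might also infer an undeclared departure from the protocol, since SAP Section 2 does not list the narrower window. That is not established: the protocol does not define the observation period and leaves the detail to the SAP.

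What the objection does not answer is that the sentences conflict and that no SOC/PT table is named for an all-event version.

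**Conclusion.** The point holds as a contradiction in SAP 4.3.2.2 and a gap in tabulation. On the evident reading, SAEs and fatal AEs starting more than one day after the last dose are, in the RTP, counted by arm only in the Overall Summary, without SOC/PT. In OLP patients who are not randomised they enter no named summary table. It would be wrong to say that such events go unreported.

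The window is 6 days nominally for a completer (5 to 7, and up to 14 with the holiday EOS). After an early stop it is 5 to 7 days if EOS follows the last dose administered, or 12, 19 or 26 days if the patient stays to Day 35 after a last dose on Day 22, 15 or 8. Those three stop days are illustrative. The number of events affected, and any difference between arms, cannot be worked out from the documents.

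**What to change.** In SAP 4.3.2.2:

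1. Reword the exclusion sentence so that it covers only AEs that are not on-treatment, and only the non-serious AE tables.
2. Reconcile it with the preceding sentence on SOC/PT summaries, and name the tables that are repeated for all AEs.
3. State that the SAE by SOC/PT table and the outcome-of-death by SOC/PT table are each produced twice: on-treatment, and for all events through EOS. For the RTP use SAF-RTP with the treatment allocation in SAP 3.2.2.2. For patients not randomised use SAF-OLP. These are the as-treated safety sets that the protocol specifies (8.3.2), so the tables should not be redefined by randomised arm.

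The cost is a rerun of existing table programs with a different period flag and a few more output pages. The all-event versions will show some off-drug events that may be confounded by later hyperkalemia treatment; the on-treatment versions beside them let the reader separate the two. Trial conduct and data collection do not change.
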